Appendix 3: Total Blood Volume

The following blood volumes will be withdrawn for each subject in Part A (except the food-effect cohort [planned to be Cohort A3]).

	Volume per blood sample (mL)	Planned number of blood samples	Total amount of blood (mL)
Clinical laboratory evaluations	7.5	4	30
Serology	3.5	1	3.5
GB1211 pharmacokinetics	4	14	56
Exploratory biomarker assessments (eg, serum galectin-3 and chemokine C-C motif ligand-4 [CCL4])	4	2	8
	Total:		97.5

If extra blood samples are required (as per [Sections 7.1, 7.2, and 7.3](#)), the maximum blood volume to be withdrawn per subject will not exceed the volume of a standard blood donation.

The following blood volumes will be withdrawn for each subject in the food-effect cohort of Part A (planned to be Cohort A3).

	Volume per blood sample (mL)	Planned number of blood samples	Total amount of blood (mL)
Clinical laboratory evaluations	7.5	6	45
Serology	3.5	1	3.5
GB1211 pharmacokinetics	4	28	112
Exploratory biomarker assessments (eg, serum galectin-3 and CCL4)	4	4	16
	Total:		176.5

If extra blood samples are required (as per [Sections 7.1, 7.2, and 7.3](#)), the maximum blood volume to be withdrawn per subject will not exceed the volume of a standard blood donation.

The following blood volumes will be withdrawn for each subject in Part B.

	Volume per blood sample (mL)	Planned number of blood samples	Total amount of blood (mL)
Clinical laboratory evaluations (including exploratory biomarker assessment of lipid profile and glucose)	7.5	8	60
Serology	3.5	1	3.5
GB1211 pharmacokinetics	4	27	108
Exploratory biomarker assessment - serum galectin-3	4	2	8
Exploratory biomarker assessment - insulin	4	2	8
Exploratory biomarker assessments - inflammation (eg, proinflammatory chemokines [including CCL4] and heat shock C-reactive protein [hsCRP], interleukin-12 [IL-12], and tumor necrosis factor [TNF]- α ; and other biomarkers of inflammation as required)	10	2	20
	Total:		207.5

If extra blood samples are required (as per [Sections 7.1](#), [7.2](#), and [7.3](#)), the maximum blood volume to be withdrawn per subject will not exceed the volume of a standard blood donation.

The following blood volumes will be withdrawn for each subject in Part C.

	Volume per blood sample (mL)	Planned number of blood samples	Total amount of blood (mL)
Clinical laboratory evaluations (including exploratory biomarker assessment of lipid profile and glucose)	7.5	8	60
Serology	3.5	1	3.5
Coagulation	1.8	6	10.8
GB1211 pharmacokinetics	4	22	88
Exploratory biomarker assessment - serum galectin-3	4	4	16
Exploratory biomarker assessment - insulin	4	4	16
Exploratory biomarker assessments - inflammation (eg, proinflammatory chemokines [including CCL4] and hsCRP, IL-12 and TNF- α ; other biomarkers of inflammation as required) and exploratory biomarkers of fibrosis	10	2	20
	Total:		214.3

If extra blood samples are required (as per [Sections 7.1](#), [7.2](#), and [7.3](#)), the maximum blood volume to be withdrawn per subject will not exceed the volume of a standard blood donation.

Appendix 4: Contraception Guidance

Definitions

Women of Childbearing Potential: premenopausal females who are anatomically and physiologically capable of becoming pregnant following menarche.

Women of Nonchildbearing Potential:

- 1. Surgically sterile:** females who are permanently sterile via hysterectomy, bilateral salpingectomy, and/or bilateral oophorectomy by reported medical history and/or medical records. Surgical sterilisation to have occurred a minimum of 6 weeks, or at the Investigator's discretion, prior to Screening.
- 2. Postmenopausal:** Females at least 45 years of age with amenorrhea for 12 months without an alternative medical reason with confirmatory follicle-stimulating hormone (FSH) levels of ≥ 40 mIU/mL. The amenorrhea should not be induced by a medical condition such as anorexia nervosa, hypothyroid disease or polycystic ovarian disease, or by extreme exercise. It should not be due to concomitant medications that may have induced the amenorrhea such as oral contraceptives, hormones, gonadotropin-releasing hormones, anti-oestrogens, or selective oestrogen receptor modulators.

Fertile male: a male that is considered fertile after puberty.

Infertile male: permanently sterile male via bilateral orchiectomy.

Contraception Guidance

Female Subjects

Female subjects who are of nonchildbearing potential will not be required to use contraception.

Female subjects of childbearing potential must be willing to use 2 methods (1 primary and 1 secondary method) of birth control from the time of signing the Informed Consent Form until 90 days after the Follow-up visit. Primary (non-barrier) methods of contraception include:

- hormonal injection (as prescribed)
- combined oral contraceptive pill or progestin/progestogen-only pill (as prescribed)
- combined hormonal patch (as prescribed)
- combined hormonal vaginal ring (as prescribed)
- surgical method performed at least 3 months prior to the Screening visit:
 - bilateral tubal ligation
 - Essure[®] (hysteroscopic bilateral tubal occlusion) with confirmation of occlusion of the fallopian tubes

- hormonal implant
- hormonal or non-hormonal intrauterine device
- vasectomised male partner (sterilisation performed at least 90 days prior to the Screening visit, with verbal confirmation of surgical success, and the sole partner for the female subject)

Secondary (barrier) methods of contraception include:

- male condom with spermicide
- female condom with spermicide
- over-the-counter sponge with spermicide
- cervical cap with spermicide (as prescribed)
- diaphragm with spermicide (as prescribed).

Female subjects of childbearing potential should refrain from donation of ova from Check-in (Day -1) until 90 days after the Follow-up visit.

Male Subjects

Male subjects (even with a history of vasectomy) with partners of childbearing potential must use a male barrier method of contraception (ie, male condom with spermicide) in addition to a second method of acceptable contraception from Check-in until 90 days after the Follow-up visit. Acceptable methods of contraception for female partners include:

- hormonal injection
- combined oral contraceptive pill or progestin/progestogen-only pill
- combined hormonal patch
- combined hormonal vaginal ring
- surgical method (bilateral tubal ligation or Essure[®] [hysteroscopic bilateral tubal occlusion])
- hormonal implant
- hormonal or non-hormonal intrauterine device
- over-the-counter sponge with spermicide
- cervical cap with spermicide
- diaphragm with spermicide

An acceptable second method of contraception for male subjects is vasectomy that has been performed at least 90 days prior to the Screening visit, with verbal confirmation of surgical success.

For male subjects (even with a history of vasectomy), sexual intercourse with female partners who are pregnant or breastfeeding should be avoided unless condoms are used from the time of the first dose until 90 days after the Follow-up visit. Male subjects are required to refrain from donation of sperm from Check-in until 90 days after the Follow-up visit.

Sexual Abstinence and Same-sex Relationships

For subjects who practice true abstinence, subjects must be abstinent for at least 6 months prior to Screening and must agree to remain abstinent from the time of signing the ICF until 90 days after the Follow-up visit.

A subject in a same-sex relationship at the time of signing the ICF must agree to refrain from engaging in a heterosexual relationship from the time of signing the ICF until 90 days after the Follow-up visit.

Appendix 5: Regulatory, Ethical, and Study Oversight Considerations

Regulatory and Ethical Considerations

This study will be conducted in accordance with the protocol and with the following:

- Consensus ethical principles derived from international guidelines including the Declaration of Helsinki and Council for International Organizations of Medical Sciences (CIOMS) International Ethical Guidelines.
- Applicable International Conference on Harmonisation (ICH) Good Clinical Practice (GCP) Guidelines.
- Applicable laws and regulations.

The protocol, protocol amendments, Informed Consent Form (ICF), Investigator Brochure, and other relevant documents must be submitted to an Ethics Committee (EC) by the Investigator and reviewed and approved by the EC before the study is initiated.

Any substantial protocol amendments, likely to affect the safety of the subjects or the conduct of the study, will require EC and regulatory authority (as locally required) approval before implementation of changes made to the study design, except for changes necessary to eliminate an immediate hazard to study subjects or any nonsubstantial changes, as defined by regulatory requirements.

The Investigator will be responsible for the following:

- Providing written summaries of the status of the study to the EC annually or more frequently in accordance with the requirements, policies, and procedures established by the EC.
- Notifying the EC of serious adverse events or other significant safety findings as required by EC procedures.
- Providing oversight of the conduct of the study at the site and adherence to requirements of 21 Code of Federal Regulations (CFR), ICH guidelines, the EC, European regulation 536/2014 for clinical studies (if applicable), and all other applicable local regulations.

Finances and Insurance

Financing and insurance will be addressed in a separate agreement.

Informed Consent

Prior to starting participation in the study, each subject will be provided with a study-specific ICF giving details of the study drugs, procedures, and potential risks of the study. Subjects will be instructed that they are free to obtain further information from the Investigator (or designee) and that their participation is voluntary and they are free to withdraw from the study at any time. Subjects will be given an opportunity to ask questions about the study prior to providing consent for participation.

Following discussion of the study with Clinical Research Unit personnel, subjects will sign 2 copies of the ICF in the presence of a suitably trained member of staff to indicate that they are freely giving their informed consent. One copy will be given to the subject, and the other will be maintained in the subject's records.

Subjects must be re-consented to the most current version of the ICF(s) during their participation in the study.

Subject Data Protection

Subjects will be assigned a unique identifier and will not be identified by name in electronic Case Report Forms (eCRFs), study-related forms, study reports, or any related publications. Subject and Investigator personal data will be treated in compliance with all applicable laws and regulations. In the event the study protocol, study report, or study data are included in a public registry, all identifiable information from individual subjects or Investigators will be redacted according to applicable laws and regulations.

The subject must be informed that his/her personal study-related data will be used by the Sponsor in accordance with local data protection law. The level of disclosure must also be explained to the subject. The subject must also be informed that his/her study-related data may be examined by Sponsor or Contract Research Organisation (CRO) auditors or other authorised personnel appointed by the Sponsor, by appropriate EC members, and by inspectors from regulatory authorities.

Disclosure

All information provided regarding the study, as well as all information collected and/or documented during the course of the study, will be regarded as confidential. The Investigator (or designee) agrees not to disclose such information in any way without prior written permission from the Sponsor.

Data Quality Assurance

The following data quality steps will be implemented:

- All relevant subject data relating to the study will be recorded on eCRFs unless directly transmitted to the Sponsor or designee electronically (eg, laboratory data). The Investigator is responsible for verifying that data entries are accurate and correct by electronically signing the eCRF.
- The Investigator must maintain accurate documentation (source data) that supports the information entered in the eCRF.
- The Investigator must permit study-related monitoring, audits, EC review, and regulatory agency inspections and provide direct access to source data documents.
- Covance is responsible for the data management of this study including quality checking of the data. Predefined agreed risks, monitoring thresholds, quality tolerance thresholds, controls, and mitigation plans will be documented in a risk

management register. Additional details of quality checking to be performed on the data may be included in a Data Management Plan.

- A Study Monitor will perform ongoing source data verification to confirm that data entered into the eCRF by authorised site personnel are accurate, complete, and verifiable from source documents; that the safety and rights of subjects are being protected; and that the study is being conducted in accordance with the currently approved protocol and any other study agreements, ICH GCP, and all applicable regulatory requirements.
- Records and documents, including signed ICFs, pertaining to the conduct of this study must be retained by the Investigator in the study site archive for at least 5 years after the end of the study unless local regulations or institutional policies require a longer retention period. No records may be destroyed during the retention period without the written approval of the Sponsor. No records may be transferred to another location or party without written notification to the Sponsor.

Investigator Documentation Responsibilities

All individual, subject-specific study data will also be entered into a 21 CFR Part 11-compliant electronic data capture (EDC) system on an eCRF in a timely fashion.

All data generated from external sources (eg, laboratory and bioanalytical data), and transmitted to Covance electronically, will be integrated with the subject's eCRF data in accordance with the Data Management Plan.

An eCRF must be completed for each enrolled subject who undergoes any screening procedures, according to the eCRF completion instructions. The Sponsor, or CRO, will review the supporting source documentation against the data entered into the eCRFs to verify the accuracy of the electronic data. The Investigator will ensure that corrections are made to the eCRFs and that data queries are resolved in a timely fashion by the study staff.

The Investigator will sign and date the eCRF via the EDC system's electronic signature procedure. These signatures will indicate that the Investigator reviewed and approved the data on the eCRF, data queries, and site notifications.

Publications

If on completion of the study the data warrant publication, the Investigator may publish the results in recognised (refereed) scientific journals subject to the provisions of the clinical study agreement (CSA). Unless otherwise specified in the CSA, the following process will occur:

If the Investigator expects to participate in the publication of data generated from this site, the institution and Investigator will submit reports, abstracts, manuscripts, and/or other presentation materials to the Sponsor for review before submission for publication or presentation. The Sponsor will have 60 days to respond with any requested revisions including, without limitation, the deletion of confidential information. The Investigator will act in good faith upon requested revisions, except the Investigator will delete any confidential

information from such proposed publications. The Investigator will delay submission of such publication or presentation materials for up to an additional 90 days in order to have a patent application(s) filed.

Appendix 6: Schedule of Assessments

Table 1: Schedule of Assessments – Part A (Single Dose)

Study Procedures	Screening	Treatment Period 1 (and 2 for Food-Effect Cohort)		Follow-up (5-7 days Postdose)
		Day -1	Days 1 to 3	
Informed consent	X			
Inclusion/exclusion criteria	X	X		
Demographic data	X			
Medical history	X	X ^a		
Urinary drug screen	X	X		
Alcohol breath test	X	X		
Serology	X			
Pregnancy test ^b	X	X		X
Follicle-stimulating hormone	X ^c			
Height and body weight	X			
Study residency:				
Check-in		X		
Check-out			Day 3 (48 hours postdose)	
Nonresidential visit	X			X
Study drug administration:				
GB1211 or placebo			Day 1 (0 hours) (30 minutes after starting a high-fat breakfast in Treatment Period 2 for food-effect cohort [planned to be Cohort A3])	
Pharmacokinetics:				
Blood sampling			Predose, 0.5, 1, 1.5, 2, 3, 4, 6, 8, 12, 16, 24, 36, and 48 hours postdose	
Urine sampling			Predose (spot collection) and 0 to 6, 6 to 12, 12 to 24, and 24 to 48 hours postdose	
Exploratory biomarker assessments:				

Table 1: Schedule of Assessments – Part A (Single Dose)

Study Procedures	Screening	Treatment Period 1 (and 2 for Food-Effect Cohort)		Follow-up (5-7 days Postdose)
		Day -1	Days 1 to 3	
Blood sample for biomarker assessments (eg, serum galectin-3 and CCL4)			Predose and 24 hours postdose	
Safety and tolerability:				
Adverse event recording	X	X	Ongoing	X
Prior/concomitant medication monitoring	X	X	Ongoing	X
Clinical laboratory evaluations	X	X	48 hours postdose	X
Vital sign measurements (blood pressure, pulse rate, and oral body temperature)	X		Predose, 1, 2, 4, 8, 24, and 48 hours postdose	X
12-lead ECG	X		Predose, 1, 4, 24, and 48 hours postdose	X
Telemetry			From at least -1 hour predose to 4 hours postdose	
Continuous 12-lead ECG			X ^c	
Physical examination	X	X ^d	Prior to discharge ^d	X ^d

Abbreviations: CCL4 = chemokine (C-C) motif ligand 4; ECG = electrocardiogram.

^a Interim medical history.

^b In all females. Performed in serum at Screening and in urine at all other times. A positive urine pregnancy test will be confirmed with a serum pregnancy test.

^c Monitor for 12-lead ECG recording will be worn from 2 hours predose to 25 hours postdose on Day 1. Extraction timepoints will be 60, 45, and 30 minutes predose (averaged for baseline) and at 0.5, 1, 1.5, 2, 3, 4, 6, 8, 12, and 24 postdose. Continuous 12-lead ECG recording will only be performed in the fasted treatment periods.

^d Symptom-directed physical examination.

^e In all females.

Table 2: Schedule of Assessments – Part B (Multiple Dose)

Study Procedures	Screening	Day -1	Days 1 to 11	Follow-up (5-7 days Post-Final Dose)
Informed consent	X			
Inclusion/exclusion criteria	X	X		
Demographic data	X			
Medical history	X	X ^a		
Urinary drug screen	X	X		
Alcohol breath test	X	X		
Serology	X			
Pregnancy test ^c	X	X		X
Follicle-stimulating hormone	X ^f			
Height and body weight	X	X ^e		X ^e
Study residency:				
Check-in		X		
Check-out			Day 11 (24 hours postdose)	
Nonresidential visit	X			X
Study drug administration:				
GB1211 or placebo			Day 1 to 9 (0 and 12 hour) and Day 10 (0 hour) ^b	
Pharmacokinetics:				
Blood sampling			Day 1: pre-am dose, 0.5, 1, 1.5, 2, 3, 4, 6, 8, and 12 hours post-am dose Days 4 to 9: pre-am dose Day 10: predose, 0.5, 1, 1.5, 2, 3, 4, 6, 8, 12 hours post-final dose Day 11: 24 hours post-final dose	
Exploratory biomarker assessments:				

Table 2: Schedule of Assessments – Part B (Multiple Dose)

Study Procedures	Screening	Day -1	Days 1 to 11	Follow-up (5-7 days Post-Final Dose)
Serum galectin-3			Day 1: pre-am dose Day 10: predose	
Fasting glucose and insulin			Day 1: pre-am dose Day 10: predose	
Lipid profile (eg, LDL, HDL, total cholesterol, and triglycerides)			Day 1: pre-am dose Day 10: predose	
hsCRP, IL-12, TNF- α , MCP-1 and proinflammatory chemokines (CCL2, CCL3, CCL4, and the chemokine receptors CCR1 and CCR2); and other biomarkers of inflammation as required			Day 1: pre-am dose Day 10: predose	
Safety and tolerability:				
Adverse event recording	X	X	Ongoing	X
Prior/concomitant medication monitoring	X	X	Ongoing	X
Clinical laboratory evaluations	X	X	Days 4 and 6: pre-am dose Day 11: 24 hours post-final dose	X
Vital sign measurements (blood pressure, pulse rate, and oral body temperature)	X		Day 1: pre-am dose, 2, 4, and 8 hours post-am dose Days 2 to 9: pre-am dose Day 10: predose, 2, 4, and 8 hours post-final dose	X
12-lead ECG	X		Day 1: pre-am dose and 4 hours post-am dose Day 5: pre-am dose and 4 hours post-am dose Day 10: predose and 4 hours post-final dose	X
Physical examination	X	X ^d	Prior to Discharge on Day 11 ^d	X ^d

Abbreviations: CCL = chemokine (C-C motif) ligand; CCR = chemokine (C-C motif) ligand receptor; ECG = electrocardiogram; HDL = high density lipoprotein; hsCRP = heat shock C-reactive protein; IL = interleukin; LDL = low density lipoprotein; MCP1 = monocyte chemotactic protein-1; TNF- α = tumor necrosis factor-alpha.

^a Interim medical history.

^b Timings relative to dose administration on Day 1.

^c In all females. Performed in serum at Screening and in urine at all other times. A positive urine pregnancy test will be confirmed with a serum pregnancy test.

^d Symptom-directed physical examination.

^e Body weight only.

^f In all females.

Table 3: Schedule of Assessments – Part C (Multiple Dose in Subjects with Suspected NASH and Liver Fibrosis)

Study Procedures	Screening	Day -1	Days 1 to 43	Follow-up (5-7 days Post-Final Dose)
Informed consent	X			
Inclusion/exclusion criteria	X	X		
Demographic data	X			
Medical history	X	X ^a		
Urinary drug screen	X	X		
Alcohol breath test	X	X		
Serology	X			
Pregnancy test ^c	X	X		X
Follicle-stimulating hormone	X ⁱ			
Height and body weight	X	X ^g		X ^g
Fibroscan CAP or Ultrasound ^e	X			
Site staff to query alcohol consumption prior to site visits ^f			At each site visit	X
Study residency:				
Check-in		X	Day 41	
Check-out			Day 2 and Day 43 (24 hours post-final dose)	
Nonresidential visit	X		Days 7, 14, 21, 28, and 35	X
Study drug administration:				
GB1211 or placebo			Days 1 to 41 (0 and 12 hour) and Day 42 (0 hour) ^b	
Pharmacokinetics:				
Blood sampling			Day 1: pre-am dose, 0.5, 1, 1.5, 2, 3, 4, 6, 8, and 12 hours post-am dose Day 2: pre-am dose (24 hours post Day 1 am dose) Day 42: predose, 0.5, 1, 1.5, 2, 3, 4, 6, 8, 12 hours post-final dose Day 43: 24 hours post-final dose	

Table 3: Schedule of Assessments – Part C (Multiple Dose in Subjects with Suspected NASH and Liver Fibrosis)

Study Procedures	Screening	Day -1	Days 1 to 43	Follow-up (5-7 days Post-Final Dose)
Exploratory biomarker assessments:				
Serum galectin-3			Day 1: pre-am dose Day 14, 28, and 42 ^h	
Fasting glucose and insulin			Day 1: pre-am dose Days 14, 28, and 42 ^h	
Lipid profile (eg, LDL, HDL, total cholesterol, and triglycerides)			Day 1: pre-am dose Days 14, 28, and 42 ^h	
hsCRP, IL-12, TNF- α , MCP-1, and proinflammatory chemokines (CCL2, CCL3, CCL4, and the chemokine receptors CCR1 and CCR2); and other biomarkers of inflammation as required			Day 1: pre-am dose Day 42 ^h	
Exploratory biomarkers of fibrosis (including but not limited to extracellular matrix proteins [TIMP-1, HA, and P3NP], A9, ELF panel, CK18, PAI-1, CH3L1, IL6, pro-collagen 3)			Day 1: pre-am dose Day 42 ^h	
Safety and tolerability:				
Adverse event recording	X	X	Ongoing	X
Prior/concomitant medication monitoring	X	X	Ongoing	X

Table 3: Schedule of Assessments – Part C (Multiple Dose in Subjects with Suspected NASH and Liver Fibrosis)

Study Procedures	Screening	Day -1	Days 1 to 43	Follow-up (5-7 days Post-Final Dose)
Clinical laboratory evaluations (including HbA1c and coagulation profile)	X	X	Day 14 and Day 28: pre-am dose Day 43: 24 hours post-final dose	X
Vital sign measurements (blood pressure, pulse rate, and oral body temperature)	X		Day 1: pre-am dose, 4, and 8 hours post-am dose Day 2: pre-am dose Days 7, 14, 21, 28, and 35 Day 42: predose, 4, 8 hours post-final dose Day 43: 24 hours post-final dose	X
12-lead ECG	X		Day 1: pre-am dose and 4 hours post-am dose Days 14 and 28 Day 42: predose, 4 hours post-final dose Day 43: 24 hours post-final dose	X
Physical examination	X	X ^d	Day 1 ^d	X ^d

Abbreviations: CAP = Controlled Attenuation Parameter; CCL = chemokine (C-C motif) ligand; CCR = chemokine (C-C motif) ligand receptor; CH3L1 = chitinase-3 like protein-1; CK18 = cytokeratin 18; ECG = electrocardiogram; ELF = E74-like transcription factors; HA = hyaluronic acid; HbA1c = glycosylated haemoglobin; HDL = high density lipoprotein; hsCRP = heat shock C-reactive protein; IL = interleukin; LDL = low density lipoprotein; MCP1 = monocyte chemotactic protein-1; P3NP = aminoterminal peptide of pro-collagen III; PAI-1 = plasminogen activator inhibitor-1; NASH = nonalcoholic steatohepatitis; TIMP-1 = tissue inhibitor of matrix metalloproteinase-1; TNF- α = tumor necrosis factor-alpha.

^a Interim medical history.

^b Timings relative to dose administration on Day 1.

^c In all females. Performed in serum at Screening and in urine at all other times. A positive urine pregnancy test will be confirmed with a serum pregnancy test.

^d Symptom-directed physical examination.

^e Fibroscan only to be performed in subjects who do not have documented history of fatty liver.

^f Site to query whether subject has consumed alcohol within 36 hours of the site visit; and whether alcohol consumption has been limited to 2 units per day on all other days of study. Protocol deviations to be recorded if subject has not.

^g Body weight only.

^h Post dosing samples for biomarkers should be collected at approximately the same time each visit.

ⁱ In all females.

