2.2. Endpoints

2.2.1. Primary Endpoints

The primary safety endpoints for the study are as follows:

- incidence and severity of adverse events (AEs)
- incidence of laboratory abnormalities, based on haematology, clinical chemistry, and urinalysis test results
- 12-lead ECG parameters
- vital signs measurements
- physical examinations

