3.1.3. Part C (Optional)

Part C will comprise a multiple-dose cohort of 25 subjects with suspected NASH and liver fibrosis (Cohort C1). Part C may start following review of data from Part A and at least 1 Part B cohort.

Potential subjects will be screened to assess their eligibility to enter the study within 28 days prior to the first dose administration. Each subject will participate in 1 treatment period only and reside at the CRU from Day -1 (the day before dosing) until the morning of Day 2, returning for nonresidential visits on Days 7, 14, 21, 28, and 35. Subjects will then check back into the CRU on Day 41 until the morning of Day 43 (24 hours after the final dose on Day 42).

[figure not shown]
All subjects will return for a Follow-up visit 5 to 7 days after their final dose.

Dose Regimen:

For Part C, Cohort C1, 15 subjects will receive GB1211 and 10 subjects will receive placebo. The dietary state for dosing in Part C will be fasted unless data from the food-effect cohort is available and supports dosing in the fed state. For all subjects, the planned dosing will be BID on Days 1 to 41 inclusive, and a final single dose administration will occur in the morning of Day 42. The total daily dose administered, dose interval/frequency, and dosing duration will be based on review of data from Parts A and B.

An overview of the study design is shown in [Figure 6](#).

Figure 6: Study Schematic (Part C)

Abbreviations: BID = twice-daily; CRU = Clinical Research Unit

The dose level of Part C is to be determined following completion of Part A and at least 1 cohort of Part B.

The total duration of study participation for each subject (from Screening through Follow-up visit) for Cohort C1 is anticipated to be approximately 11 weeks.

A Schedule of Assessments is presented in [Appendix 6](#).

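### Part C schedules no physical examination, a listed primary safety endpoint, from Day 2 until Follow-up on Day 47 to 49; unlike Parts A and B, it has none at final discharge

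*Protocol*

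**What the plan says.** Protocol Section 2.2.1 lists "physical examinations" among five primary safety endpoints for the whole study. Section 7.3.5 leaves their timing to Appendix 6 and says that a full examination is usually done only at Screening.

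In Appendix 6 the examination in the dosing-period column is placed as follows:

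- Table 1 (Part A): "Prior to discharge ^d", with check-out on Day 3, 48 h after the dose.
- Table 2 (Part B): "Prior to Discharge on Day 11 ^d", which is 24 h after the final dose on Day 10.
- Table 3 (Part C): the whole row reads "Physical examination X X ^d Day 1 ^d X ^d". The only entry in the dosing-period column is Day 1.

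Footnote d is the same in all three tables: "Symptom-directed physical examination". Part C dosing is given as "Days 1 to 41 (0 and 12 hour) and Day 42 (0 hour) ^b", and check-out as "Day 2 and Day 43 (24 hours post-final dose". Section 3.1.3 adds: "All subjects will return for a Follow-up visit 5 to 7 days after their final dose".

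**The concern.** Part C is the only patient group and has the longest planned exposure, and its safety is a primary objective in its own right. It is also the only part in which subjects leave the unit after the last dose without a scheduled examination. Logistics do not explain this, because subjects are resident from Day 41 to the morning of Day 43. Three of the other primary safety measures (laboratory tests, vital signs and ECG) are taken on Day 43.

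What could be lost is a physical sign that is present late in treatment and gone within a week of stopping. The protocol itself relies on signs of this kind: the liver-related criterion in Section 4.8 refers to right upper quadrant tenderness and rash.

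**Working it through.** There is no stated figure to reproduce. The check is a day count and a comparison of the three schedules.

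**Inputs.** Part C dosing is twice daily on Days 1 to 41 with one dose on Day 42 (Appendix 6, Table 3). Follow-up is 5 to 7 days after the final dose (Section 3.1.3). The examination rows and check-out times come from Tables 1 to 3. Cohort C1 has 25 subjects (15 active, 10 placebo; Section 3.1.3).

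**Part C gap.**

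1. Follow-up day = 42 + 5 to 42 + 7 = Day 47 to Day 49.
2. Interval from the Day 1 examination to the next scheduled one = 47 − 1 to 49 − 1 = 46 to 48 days.
3. Dosing days with a scheduled examination = 1 (Day 1). Dosing days without = 42 − 1 = 41 (Days 2 to 42).
4. Planned doses = 41 × 2 + 1 = 83. Doses after Day 1 = 83 − 2 = 81.
5. The Day 1 cell gives no time relative to dose, although the Day 1 vital-sign and ECG cells do. If the examination is before the morning dose, all 83 doses fall between it and Follow-up. If it is after both Day 1 doses, 81 do.

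**Comparison across parts.**

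| | Part A | Part B | Part C |
|---|---|---|---|
| Final dose | Day 1 (each period) | Day 10 | Day 42 |
| Final check-out | Day 3 | Day 11 | Day 43 |
| Examination before that check-out | Yes, about 48 h after dose | Yes, about 24 h after dose | None |
| Follow-up | Day 1 + 5 to 7 = Day 6 to 8 | Day 10 + 5 to 7 = Day 15 to 17 | Day 47 to 49 |

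**Within Part C, at Day 43 (24 h after the final dose).** Clinical laboratory evaluations: yes. Vital signs: yes. 12-lead ECG: yes. Physical examination: no.

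**Whether another section fills the gap.** Section 7.3.5 points back to Appendix 6. The SAP (Section 6.3) states that it covers Parts A and B only. Section 7.3 allows extra assessments if clinically appropriate but schedules none.

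**The case against.** The strongest case on the other side has four parts.

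- **Symptoms are sought throughout.** Every examination after Screening is symptom-directed. Section 7.3.1 requires open questioning at least daily while subjects are resident and at each visit, which covers Days 7, 14, 21, 28 and 35 and the Day 41 to 43 stay. Section 7.3 provides for unscheduled assessments, and an unfavourable sign is itself an adverse event under Appendix 1. This stands, and it narrows the loss to signs that prompt no complaint. Even a symptom-directed discharge examination might miss some of those. It does not remove the point, because Parts A and B have the same provisions and still schedule an examination at discharge.
- **Day 1 is a dosing day.** A reader might infer that no examination takes place across the 42 dosing days. Table 3 does not support that, since one is scheduled on Day 1. Examinations on dosing days are not the standard in the other parts either: the Part A and Part B discharge examinations fall after the dosing day or days. The departure in Part C is the missing end-of-treatment examination.
- **The purpose of the Day 1 examination is unknown.** A reader might call it a second baseline one day after Day -1, or a slip for the discharge day. The documents show neither. Subjects stay until the morning of Day 2, so it could follow the first dose.
- **No analysis depends on matching schedules.** A reader might infer that the Part C data cannot be compared with those of Parts A and B. Section 8.5 plans descriptive safety summaries only, and no comparison between parts is specified. Part C has its own placebo group on the same schedule. All that can be said is that Part C lacks the matching end-of-treatment time point.

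**Conclusion.** The point holds as a gap in the Part C assessment schedule. No physical examination is scheduled from Day 2 until Follow-up on Day 47 to 49, which leaves out 41 of 42 dosing days and the Day 43 check-out for all 25 planned subjects. Parts A and B have a discharge examination, and the Part C laboratory tests, vital signs and ECG have a Day 43 assessment. No other section supplies one or explains its absence.

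The consequence is modest. A sign at the end of treatment would escape the scheduled examinations only if it also prompts no complaint and clears before Follow-up. The documents do not allow the frequency of such signs to be estimated. The endpoint is not empty: a symptom-directed examination is scheduled at Follow-up, and unscheduled ones are permitted. The day counts assume the planned Part C regimen, whose frequency and duration may change after review of Parts A and B.

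**What to change.** Reconcile the Part C row in Appendix 6, Table 3 with Tables 1 and 2 by scheduling the symptom-directed examination prior to discharge on Day 43. There are two ways to do it:

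- **Move the Day 1 examination to Day 43.** The number of examinations is unchanged and Day -1 remains as baseline. The cost is the loss of the only examination scheduled on the first dosing day in the patient cohort.
- **Keep Day 1, state whether it is before or after the dose, and add Day 43.** The cost is one brief examination per subject (25 × 1 = 25 in all).

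Neither needs an extra visit, because subjects are resident until the Day 43 check-out. If the Day 1 placement is deliberate, a sentence in Section 7.3.5 should give the reason. If the Part C dosing duration is changed, the examination should stay tied to the final check-out and not to a fixed day number.
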